### M0 Phase

During the M0 Phase, there are 2 types of visits. Post-baseline imaging studies are not required in the M0 Phase and are performed if the investigator determines imaging study(ies) is/are needed to assess development of metastases (M1 CRPC). Depending on the timing of an imaging study, its results may be recorded as part of the 6-month M0 Phase study visit or part of an M0 Phase imaging visit, as described below:

- **6-month M0 Phase study visit:** A scheduled 6-month M0 Phase study visit (office visit), will occur every 6 months ( $\pm$  1 month), starting from the date of the patient's registration, until 3 years after the last patient is registered. Any imaging study that occurs within 1 month of a 6-month M0 Phase study visit will be considered part of that 6-month M0 Phase study visit, and no repeat study assessments will be required.
- **M0 Phase imaging visit:** This visit occurs if, outside of the 1-month window for the 6-month M0 Phase study visit, the investigator determines imaging study(ies) is/are needed to assess development of metastases (M1 CRPC).

The choice of imaging modality will depend on the study site's standard of care; the same modality should be used for all images for a given patient until diagnosis of M1 CRPC. However, if the modality is changed to one with greater sensitivity (e.g., Tc 99m to NaF PET/CT or MRI) and diagnosis of M1 CRPC occurs at first use of a new imaging modality, an additional imaging study with the previous modality will be performed within 1 month after the positive imaging study; this additional imaging study will be reimbursed by the sponsor. However, if the modality is changed to one with lower sensitivity, an imaging study with the previous higher modality will not be performed.

Assessments for both types of M0 Phase visits include: ECOG performance status, current opioid analgesic use (yes/no), pain status (with BPI), prostate cancer interventions since the previous visit, survival status, blood samples for clinical laboratory tests (alkaline

phosphatase, hemoglobin, LDH, serum albumin, and serum PSA) and for AOR (if patient has consented to AOR), and safety events (serious adverse events [SAEs], see Safety Measures, below); all such data that have become available since the previous visit will also be collected.

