### **5.3 Removal of Patients from the Study**

Whenever possible, patients should remain in the study and continue with protocol-specified assessments. A patient may be withdrawn from the study if, in the investigator's clinical judgment, it is in the best interests of the patient.

Patients may discontinue their participation in the study at any time without prejudice toward their future medical care. A patient may choose to discontinue all evaluations and participation (including survival follow-up), or may discontinue all study evaluations with the exception of being followed for survival. If a patient chooses to withdraw from the study, the investigator should make every reasonable attempt to confirm the status of all ongoing SAEs meeting the criteria defined in Section 7.6.18. The date and reason for withdrawal will be recorded in the source documentation and on the eCRF.

If a patient fails to respond to requests for follow-up, the study site will (at a minimum) send a registered letter to the patient requesting contact. All attempts to resume contact (including copies of written correspondence) will be included in the source documentation. Patients who do not respond to requests for follow-up after all reasonable attempts to establish contact will be considered lost to follow-up. Data on all patients who withdraw consent or are determined to be lost to follow-up will be reviewed by the investigator through the National Death Index (NDI) or Social Security Death Index (SSDI) to ascertain any deaths not reported in the study. The date of death, when available, will be gathered from the NDI or SSDI and recorded on the eCRF.

Any patient who is not diagnosed with M1 CRPC and receives at least 1 partial ( $> 0$  mL) infusion of Provenge during the study will be withdrawn from the study. Serious adverse events that occur in such patients will be recorded as described in Section 7.6.18.

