### 7.3 Scheduled 6-Month M0 Phase Study Visit

For patients in the M0 Phase, scheduled visits will occur every 6 months ( $\pm$  1 month), starting 6 months from the date of the patient's registration, and will continue until 3 years after the last patient is registered. All data that have become available since the previous visit regarding the parameters listed below will be collected. Imaging studies are optional and will be determined by investigator assessment of need. Any imaging study that occurs within 1 month of a 6-month M0 Phase study visit will be considered part of that 6-month M0 Phase study visit, and no repeat assessments will be required.

The following will occur at each scheduled 6-month M0 Phase study visit:

- ECOG performance status.
- Current opioid analgesic use (yes/no).
- Pain status (with BPI).
- Prostate cancer interventions as described in Section [7.6.13](#).
- Survival status. The terms "alive" with the date of confirmation, "deceased", or "unconfirmed" are collected. For those patients recorded as "deceased", an additional eCRF page entitled "Date and Cause of Death" will become available. On this page, "Date of death" and "Cause of Death (check all that apply): Disease progression, Cardiac event, New primary cancer, Cerebrovascular event, and other (specify)", are listed as choices.
- Bone and soft tissue imaging studies for detection of metastatic prostate cancer (optional).
- Blood sample for clinical laboratory tests at local laboratory, as indicated in the Schedule of Assessments ([Table 1](#)).
- Serious adverse events in patients who receive at least 1 partial ( $> 0$  mL) infusion of Provenge that occur  $\leq$  30 days after the last infusion, regardless of relationship to Provenge;
- Blood sample for biomarker analysis, providing the patient has consented to AOR. This sample is collected within  $\pm$  1 month of an imaging study if it occurs during the  $\pm$  1 month visit window.

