## 7.5 M1 Phase Data Collection

The M1 Phase will be observational. For patients in M1 Phase, data will be collected every 6 months ( $\pm 1$  month) until 5 years after the last patient is registered.

At each 6-month time point during M1 Phase, all data that have become available since the previous time point regarding the parameters listed below will be collected. For patients who enter M1 Phase because of an M0 Phase study visit that includes an imaging study positive for M1, all such data that have become available since the last scheduled 6-month M0 Phase study visit will be collected.

The data to be collected during M1 Phase include:

- ECOG performance status.
- New sites of metastases.
- ACE-27 assessment (for those patients who enter M1 Phase because of an M0 Phase study visit that includes an imaging study positive for M1, an ACE-27 is required to be completed within 6 months after the patient's last M0 phase study visit).
- Current opioid analgesic use (yes/no).
- Prostate cancer interventions as described in Section [7.6.13](#).
- Survival status as described in Section [7.6.14](#).

- Clinical laboratory results (alkaline phosphatase, hemoglobin, LDH, serum albumin, and serum PSA).
- Serious adverse events in patients who receive at least 1 partial ( $> 0$  mL) infusion of Provenge that occur  $\leq 30$  days after the last infusion, regardless of relationship to Provenge.

Data collection during M1 Phase may occur by clinic visits, reviews of the patient's medical record, or telephone calls, with the call documented in the patient's medical record. Clinic visits or telephone calls may occur by the following methods:

- Patient visit at the study site.
- Telephone call from the study site to the patient's physician.
- Telephone call between the study site and the patient.

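### M0 follow-up has no record-review or telephone route and no M1 follow-up for men who stop visits, so some M1 events go unsought and the yes/no analysis of future positive imaging is exposed to bias of unknown direction

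*Combined protocol and SAP*

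**What the plan says.** Section 4.0 describes M0 follow-up through two kinds of visit. For the first, "A scheduled 6-month M0 Phase study visit (office visit), will occur every 6 months"; the second is an imaging visit when the investigator judges one necessary. Sections 7.3 and 7.4 repeat this, and none of the three offers another means of contact. At a visit that takes place, collection is cumulative: "All data that have become available since the previous visit regarding the parameters listed below will be collected" (7.3), and imaging is among those parameters.

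The M1 Phase is more flexible: "Data collection during M1 Phase may occur by clinic visits", by record review, or by telephone, including a call to the patient's physician (7.5).

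Section 5.3 encourages retention: "Whenever possible, patients should remain in the study and continue with protocol-specified assessments". A man who stops may leave entirely, or he "may discontinue all study evaluations with the exception of being followed for survival". "Patients who do not respond to requests for follow-up after all reasonable attempts to establish contact will be considered lost to follow-up". For withdrawn and lost men the only outside source is the national death indexes, used "to ascertain any deaths not reported in the study".

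Section 8.3.2 analyses future positive imaging in the M0 population as yes/no over all post-baseline time, with Cox regression as a supplement. It does not say how men with incomplete follow-up are handled. In 8.3.3, MFS counts M1 or death as the event and censors other men when M1 status was last determined. The SAP was never finalized, so no later document fills the gap.

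**The concern.** The second secondary objective depends on learning of M1 after baseline. Imaging in the M0 Phase is at the investigator's discretion, and follow-up lasts roughly 3 to 5 years per man (2 years of accrual, then 3 years after the last registration). M1 is therefore recorded only while contact continues. The flexible collection methods begin only after M1 has been identified, which is after the M0 endpoint has occurred.

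If a man stops attending for good around the time he progresses, his M1 is not sought. If that happens more often at one level of a predictor than at the other, the estimated association shifts. The purpose of the analysis is to identify and weight predictors, so such a shift affects the result itself as well as its precision.

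**Working it through.** **The plan's own figure.** The only power statement concerns the primary baseline endpoint: 34.95% vs 29.05%, 1000 men per level, two-sided alpha 0.05. The odds ratio is (0.3495/0.6505)/(0.2905/0.7095) = 1.312, as stated. With power = Φ[(√n·|p1−p2| − 1.96·√(2p̄q̄)) / √(p1q1+p2q2)], power is 80.8%, against the stated 80%. The figure reproduces and does not depend on follow-up. The documents give no event count, power or dropout rate for the M0 endpoint, so everything below is illustrative.

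**Size of the M0 population.** The protocol expects a baseline M1 rate similar to 32%: 2000 × (1 − 0.32) = 1360 men, or 680 per level of an evenly split predictor.

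**Cox regression, loss at progression.** Suppose a share p of progressing men leave at progression and their M1 is never recorded. The hazard of a recorded event is then λ(1 − p), so the observed HR is HR × (1 − p_high)/(1 − p_low). With an assumed true HR of 1.5:

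| Loss, low vs high risk | Calculation | Observed HR |
|---|---|---|
| 5% vs 15% | 1.5 × 0.85/0.95 | 1.34 |
| 5% vs 20% | 1.5 × 0.80/0.95 | 1.26 |
| 10% vs 25% | 1.5 × 0.75/0.90 | 1.25 |
| Equal | ratio of 1 | 1.50 |
| 15% vs 5% (reversed) | 1.5 × 0.95/0.85 | 1.68 |

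Simulations with 1360 men and 6-monthly detection agree:
- 5% vs 15% gave HR 1.36, against 1.48 with no loss (60 replicates, 3 to 5 years of follow-up).
- Equal loss of 15% or 25% gave 1.51 or 1.50 (100 replicates).
- Reversed loss gave 1.68 (100 replicates).

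If record review recovers 80% of the lost men (assumed), the three unequal losses fall to 1% vs 3%, 1% vs 4% and 2% vs 5%. The HR is then 1.5 × 0.97/0.99 = 1.47, 1.5 × 0.96/0.99 = 1.45 and 1.5 × 0.95/0.98 = 1.45.

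**Yes/no logistic analysis.** Assume true M1 of 40% vs 30% in 680 men per level, and that a missed M1 is entered as no. The observed proportion is p × (1 − share missed).

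| Missed, high vs low risk | Observed proportions | OR | Power |
|---|---|---|---|
| None | 0.400 vs 0.300 | 1.56 | 97% |
| 10% vs 10% | 0.360 vs 0.270 | 1.52 | 95% |
| 15% vs 5% | 0.340 vs 0.285 | 1.29 | 59% |
| 5% vs 15% | 0.380 vs 0.255 | 1.79 | 99.9% |

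At 15% vs 5%, the events missed are 680 × 0.40 × 0.15 + 680 × 0.30 × 0.05 = 40.8 + 10.2 = 51, out of 272 + 204 = 476. With 80% recovery the proportions are 0.388 vs 0.297 and the OR is (0.388/0.612)/(0.297/0.703) = 1.50.

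**Dropout before progression.** A simulated Cox model (40,000 men, 4 years, hazard 0.15 per year at the low level, predictor HR 1.8, an unmeasured risk factor in 30% of men that doubles the hazard) gave these results:
- No dropout: HR 1.77, yes/no OR 2.46.
- Dropout of 0.05 vs 0.20 per year, low vs high level: HR 1.75, OR 1.32.
- The same, with dropout also tripled by the unmeasured factor: HR 1.66, OR 1.07.
- Dropout rates reversed: HR 1.77, OR 3.41.

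The Cox estimate is fairly robust to this kind of loss. The yes/no odds ratio is not.

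**The case against.** A reader might infer that any M1 found after a missed visit or a change of provider is never captured. The documents do not support that. One later attended visit brings in all interim imaging, changing provider is not withdrawal, and a positive study at any time in the M0 Phase moves the man into the M1 Phase, where record review and telephone already apply. Record review in the M0 Phase is not forbidden; it is simply not provided for. The gap is confined to men who stop permanently before the site learns of a positive scan.

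A reader might also infer that high-risk predictors are attenuated. That requires progressing high-risk men to leave more often than progressing low-risk men, which no passage establishes. Loss that depends on progression alone, equal across levels, leaves the HR unchanged. The illustrative HRs largely restate the assumed loss rates.

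Nor does 8.3.2 say that a man with incomplete follow-up is entered as no; it is silent. In MFS, deaths found through the indexes can still count, so some unseen M1 becomes a later event and is not lost altogether.

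Finally, office visits have a purpose. M0 visits include blood tests, the BPI and optional biomarker samples, whereas no study blood is drawn in the M1 Phase. An office visit is a sensible default.

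All of this stands. It limits the claim about bias, but it supplies no route to M1 status for a man who has stopped attending.

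**Conclusion.** The gap holds in limited form. For any M0 man who permanently stops attending and then progresses without the site knowing, the plan makes no provision to seek his M1. The loss of that event for the secondary endpoint, and its loss or delay in MFS, follow from the text. The direction and size of any bias do not: they rest on assumed loss rates and could be toward the null, absent in the Cox HR, or away from the null. The most exposed analysis is the yes/no logistic one, where an assumed 15% vs 5% loss takes the OR from 1.56 to 1.29 if missed M1 is entered as no. The primary analysis is untouched. This is worth correcting because a secondary objective is affected and the remedy is cheap; it does not undermine the study as a whole.

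**What to change.** - **4.0 and 7.3:** keep the office visit as the default, but allow a missed M0 visit to be completed by record review or telephone, as 7.5 does. Cover imaging dates and results, interventions, available laboratory and PSA values, and survival.
- **5.3:** add an option, with the patient's consent, of record-based follow-up of imaging or M1 status and interventions alongside survival.
- **8.3.2 and the MFS definition in 8.3.3:** count M1 found by these routes as an event.
- **8.3.2:** state how men with incomplete follow-up are handled, and do not enter them as no without accounting for follow-up time. One way is to make the Cox analysis the main one for this endpoint.

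The cost is modest site time, using a method the protocol already provides for in the M1 Phase, plus protocol and consent wording. BPI scores and optional biomarker blood would still be missing for visits completed this way.

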### M1 Phase

M1 Phase is observational. Patients will enter M1 Phase when diagnosed with M1 CRPC at registration or at any M0 Phase study visit. Patients identified with an imaging study positive for M1 disease anytime during the M0 Phase will enter M1 Phase and begin following the schedule of assessments for M1 Phase starting at the next 6-month visit. For those patients who enter M1 Phase because of a positive imaging study during M0 Phase, an ACE-27 is required to be completed within 6 months after the patient's last M0 Phase visit.

During M1 Phase, data will be collected (via clinic visits, reviews of the patient's medical record, and/or telephone calls) every 6 months ( $\pm$  1 month) until 5 years after the last patient is registered. At each 6-month time point during M1 phase, all data that have become available since the previous time point will be collected regarding ECOG performance status, new sites of metastases, current opioid analgesic use (yes/no), prostate cancer interventions, survival status, clinical laboratory (alkaline phosphatase, hemoglobin, LDH, serum albumin, and serum PSA) data, and safety events (SAEs, see Section [7.6.18](#)).

In interventional clinical trials, the Prostate Cancer Working Group currently recommends measurement of serum PSA levels every 3 or 4 weeks and CT or MRI every 12 weeks to assess disease progression ([Scher 2008](#)). During M1 Phase, the sponsor anticipates patients will be monitored similarly. The sponsor acknowledges that each M1 Phase patient will receive care appropriate for the treatment being administered and the standard of care in the investigator's clinical practice. At each 6-month time point for data collection during M1 Phase, all prostate cancer interventions administered during the prior 6-month period, including indication(s) for choice of therapy, starting dose, timing (start and stop dates), and rationale for starting and stopping therapy (e.g., PSA progression), will be recorded on the electronic case report form (eCRF).

The anticipated duration of the study is at least 7 years, including 2 years for accrual and up to 5 years for follow-up after the last patient is registered.

The Schedule of Assessments is presented in [Table 1](#).

## **5.0 STUDY POPULATION**

Men with CRPC and no known M1 disease who are at least 18 years of age at baseline are eligible. A minimum of 2000 patients will be registered in this trial. Patients must meet the following eligibility criteria to be registered in the study:

## **5.1 Inclusion Criteria**

- 5.1.1. Written informed consent obtained prior to the initiation of study procedures.
- 5.1.2. Men  $\geq 18$  years of age.
- 5.1.3. Histologically documented prostatic adenocarcinoma confirmed by a pathology report from prostate biopsy or a RP specimen. Patients whose pathology reports are no longer available may be enrolled if, in the opinion of the investigator, the patient has a clinical course consistent with prostatic adenocarcinoma.
- 5.1.4. History of CRPC: A sequence of 2 rising serum PSA values compared to the single lowest serum PSA value (nadir), measured at least 7 days apart where the second value is  $\geq 2$  ng/mL (Scher 2008), in the setting of surgical or continuous medical castration (defined as testosterone  $\leq 50$  ng/dL with either a luteinizing hormone-releasing hormone [LHRH] agonist or antagonist as monotherapy). Patients who subsequently receive combination and/or secondary hormonal treatments (e.g., combined androgen blockade [CAB]) that reduce or control serum PSA elevation are considered to have CRPC and are eligible.

## **5.2 Exclusion Criteria**

- 5.2.1. Known M1 disease: Previous imaging studies have been positive for bone or visceral metastases, or for lymph nodes having a measurable diameter  $\geq 2$  cm. A prostate mass or recurrence solely in the prostate bed is not considered metastatic disease (Scher 2008).
- 5.2.2. Undergone imaging study for metastatic prostate cancer  $\leq 3$  months prior to the date written informed consent is obtained. Patients with previous imaging studies may enter this trial  $> 3$  months after their last imaging study if at that time they meet all eligibility criteria.
- 5.2.3. ECOG performance status  $\geq 3$ .
- 5.2.4. Known malignant pleural effusions or ascites.
- 5.2.5. Current or prior treatment with investigational therapy for M0 CRPC, Taxotere (docetaxel), Provenge® (sipuleucel-T), Zytiga (abiraterone acetate), Xtandi (enzalutamide), Jevtana (cabazitaxel), or Xofigo (radium Ra 223 dichloride).
- 5.2.6. Any medical intervention or other condition which, in the opinion of the Principal Investigator or the Medical Monitor, could compromise adherence with study requirements or otherwise compromise the study objectives.
- 5.2.7. Treatment for or history of malignancy (stage I-IV) other than prostate cancer or non-melanoma skin cancer within  $\leq 5$  years.

### **5.3 Removal of Patients from the Study**

Whenever possible, patients should remain in the study and continue with protocol-specified assessments. A patient may be withdrawn from the study if, in the investigator's clinical judgment, it is in the best interests of the patient.

Patients may discontinue their participation in the study at any time without prejudice toward their future medical care. A patient may choose to discontinue all evaluations and participation (including survival follow-up), or may discontinue all study evaluations with the exception of being followed for survival. If a patient chooses to withdraw from the study, the investigator should make every reasonable attempt to confirm the status of all ongoing SAEs meeting the criteria defined in Section 7.6.18. The date and reason for withdrawal will be recorded in the source documentation and on the eCRF.

If a patient fails to respond to requests for follow-up, the study site will (at a minimum) send a registered letter to the patient requesting contact. All attempts to resume contact (including copies of written correspondence) will be included in the source documentation. Patients who do not respond to requests for follow-up after all reasonable attempts to establish contact will be considered lost to follow-up. Data on all patients who withdraw consent or are determined to be lost to follow-up will be reviewed by the investigator through the National Death Index (NDI) or Social Security Death Index (SSDI) to ascertain any deaths not reported in the study. The date of death, when available, will be gathered from the NDI or SSDI and recorded on the eCRF.

Any patient who is not diagnosed with M1 CRPC and receives at least 1 partial ( $> 0$  mL) infusion of Provenge during the study will be withdrawn from the study. Serious adverse events that occur in such patients will be recorded as described in Section 7.6.18.

## **6.0 TREATMENTS**

No treatments will be administered as part of this study.

## **7.0 STUDY ASSESSMENTS AND PROCEDURES**

Patients will provide written informed consent and those that are eligible on the basis of inclusion/exclusion criteria will be registered in the trial and receive a unique identifier at that time.

The study assessments and procedures to be performed during the study are summarized in the Schedule of Assessments (Table 1) and described in Section 7.6.

